# II. Diagnosis & Clinical Improvement

Anxiety and Related Disorders Interview Schedule for DSM-5 (ADIS-5): This semi-structured, diagnostic clinical interview focuses on DSM-5 diagnoses of anxiety disorders and their accompanying mood states, somatoform disorders, and substance and alcohol use. The information derived from the interview using the ADIS allows clinicians to determine differential diagnoses and gain a clear understanding of the level and severity of each diagnosis. Principal and additional diagnoses are assigned a clinical severity rating (CSR) on a scale from 0 (no symptoms) to 8 (extremely severe symptoms), with a rating of 4 or above (definitely disturbing/disabling) passing the clinical threshold for DSM diagnostic criteria. Inquiries about suicidal and homicidal ideation are also part of this interview. This measure has demonstrated excellent to acceptable interrater reliability for the anxiety and mood disorders (Brown, Di Nardo, et al., 2001).

An abbreviated version of the ADIS-5 will be administered at the screening session to assess presence of current psychopathology. During treatment and the follow-up period, specific sections corresponding to those disorders identified to be clinically significant at the initial intake will be administered. Because the ADIS is routinely used for clinical and study evaluations at CARD, participants will have the option (see consent form) to consent for the use of a recent CARD evaluation (if applicable and at the discretion of the study team) to avoid repeating the diagnostic evaluation in this study (if completed within 1-month of the StAR2 screening date).

Clinical Global Impressions- Improvement & Severity (CGI- I & CGI-S): The CGI provides an overall clinician-determined summary measure that considers all available information, including

knowledge of the participant's history, psychosocial circumstances, symptoms, behavior, and the impact of the symptoms on the participant's ability to function compared to other clinical participants with similar diagnoses. The CGI comprises two companion one-item measures evaluating the following: (a) severity of psychopathology from 1 to 7, and (b) change from the initiation of treatment on a similar seven-point scale.

The CGI is administered by an experienced clinician who is familiar with the diagnoses under study and the likely progression of treatment. Consequently, the CGI rater can make an expert clinical global judgment about the severity of the illness across various time points within the context of that clinical experience. The clinician makes a judgment about the total picture of the participant at each visit: the illness severity, the participant's level of distress and other aspects of impairment, and the impact of the illness on functioning. The IE also makes CGU ratings after the post assessment, and the 1 and 6 month follow-up assessments.

**Instructions**: The CGI-Severity (CGI-S) asks the clinician one question: "Considering your total clinical experience with this particular population, how impaired is the participant at this time?" The clinician is asked to rate impairment using the following seven-point scale: 1=normal, not at all ill; 2=borderline mentally impaired; 3=mildly impaired; 4=moderately impaired; 5=markedly impaired; 6=severely impaired; 7=among the most extremely impaired participants. This rating is based upon observed and reported symptoms, behavior, and function in the past seven days. Clearly, symptoms and behavior can fluctuate over a week; the score should reflect the average severity level across the seven days.

The CGI-Improvement (CGI-I) is similar in its format. Each time the clinician completes the measure (session 4, 8, 12, 16), the clinician compares the participant's overall clinical condition to the one-week period just prior to the initiation of treatment. The CGI-S score obtained at the baseline (initiation) visit serves as a good basis for making this assessment. Again, only the following query is rated on a seven-point scale: "Compared to the participant's condition at admission to the project, this participant's condition is: 1=very much improved since the initiation of treatment; 2=much improved; 3=minimally improved; 4=no change from baseline; 5=minimally worse; 6= much worse; 7=very much worse since the initiation of treatment."

The CGI-I score generally aligns with the CGI-S such that improvement in one follows the other. Anchors for scoring, however, are quite different, and the CGI-I is based upon changes from the initiation of treatment in contrast to changes on a week-to-week basis. Consequently, the two CGI scores can occasionally be dissociated such that a clinician may notice changes in the CGI-I relative to baseline despite no recent changes in the overall CGI severity score or vice versa.

*Quality of Life Enjoyment and Satisfaction Questionnaire (Q-LES-Q)*: The Q-LES-Q is a selfreport measure that assesses the degree of satisfaction and enjoyment experienced over the past week. The measure consists of 14 items and assesses satisfaction across the following domains: physical health, mood, work, household activities, social relationships, family relationships, leisure activities, daily functioning, sexual drive and interest, economic status, living situation, physical stability, vision, and overall sense of well-being. According to Ritsner et al. (2002), the Q-LES-Q has demonstrated high internal consistency and good construct validity (Endicott, Nee, Harrison, & Blumenthal, 1993).

Adult Mental Healthy Continuum-Short Form (MHC-SF): The MHC-SF is a measure of overall positive mental health which consists of 14 items. This assessment measures emotional well-being, psychological well-being, and social well-being (Keyes et al., 2008).

## **III.** Anxiety/Mood

Overall Depression Severity and Impairment Scale (ODSIS): The ODSIS is a 5-item continuous measure assessing depression in the following domains: frequency, intensity, functional impairment in pleasurable activities, work or school, and interpersonal relationships. Items are scored on a 5-point Likert scale of 0–4. A psychometric analysis of the ODSIS scale found good internal consistency (Cronbach's alpha = .92; Bentley et al., 2014).

Overall Anxiety Severity and Impairment Scale (OASIS): The OASIS is a five-item continuous measure of anxiety-related severity and impairment. Items are coded from 0 to 4 and are summed to obtain one total score. Results from three previous psychometric evaluations of the OASIS have indicated high internal consistency, excellent test– retest reliability, and convergent and discriminant validity in clinical and nonclinical samples (Norman et al., 2006).

# Structured Interview Guide for Hamilton Anxiety Scale (SIGH-A)

**Purpose:** The purpose of this structured interview is to assist in the reliable assessment of anxiety severity by standardizing the method of assessment and providing clear anchor points for the assignment of severity ratings. The interview items and the anchor points are meant to supplement good clinical judgment, not replace it.

**Instructions:** Begin the interview with an introduction, describing the scale and its purpose in a way that is relevant for the specific participant. The first question for each item should be asked exactly as written. Often this question will elicit enough information about the severity and frequency of a symptom for the clinician to rate the item with confidence. Follow-up questions are provided, however, for use when further exploration of additional clarification of symptoms is necessary. The specified questions should be asked until there is enough information to rate the item confidently. In some cases, additional follow-up questions may be necessary to obtain information. For some of the items, there may be similar questions already asked about some of the symptoms (for a previous item). There is no need to repeat questions about these symptoms unless additional information is needed to rate the severity. The final score for each item should reflect an assessment and balancing of the severity and frequency of the symptom.

**Rating Items:** All of the items have the same anchor points. The following may be useful as guides to rating severity:

MILD: Occurs irregularly and for short periods of time.

MODERATE: Occurs more constantly and of longer duration, requiring considerable effort on the part of the subject to cope with it.

SEVERE: Continuous and dominates the subject's life.

VERY SEVERE: Incapacitation.

For each item, several defining characteristics of each severity score are provided. These defining characteristics are meant as guidelines to aid in the reliable use of the severity scales and represent examples of the severity levels appropriate to the rating. Severity is defined most readily by the frequency of occurrence, and the degree of distress and interference associated with the symptom. The number of symptoms present is included in the severity rating only as it impacts distress and interference. For example, a higher rating may be achieved for a single severe symptom and for several mild or moderate symptoms. Alternatively, several mild symptoms may lead to a moderate rating of severity because of their overall impact on distress. In addition to the guidelines for each item, the interviewer should note the following conventions for boundary problems:

**None to mild boundary**: Most questionable cases should be rated as one, as zero is meant to be an anchor point with no symptom present.

**Mild to moderate boundary**: Symptoms are endorsed less than fifty percent of the time and cause little to no interference or distress; rate as one. Symptoms are endorsed less than fifty percent of the time and are rated as causing mild to moderate interference or distress; rate as two. Symptoms are endorsed more than fifty percent of the time and are rated as causing mild interference or distress; rate as two.

**Moderate to severe boundary**: Symptoms are endorsed less than fifty percent of the time and are rated as causing severe interference or distress; rate as three. Symptoms are endorsed more than fifty-percent of the time and are rated as causing moderate to severe interference or distress, but not both; rate as three.

**Severe to very severe boundary**: Questionable cases should generally be rated as a three; ratings of four are reserved for behavioral events clearly identified by the rating anchors. To elicit the information necessary for assigning severity ratings, the interviewer must assess the frequency of occurrence, degree of distress, and degree of interference associated with symptoms. The following questions are recommended for this assessment:

Have you had the symptom every day? If NO, have you had the symptom more days than not? How much does the symptom bother you? How much does it interfere with your life?

NOTES: Time period. The ratings should be based on the participant's condition in the past week.

If the participant has panic attacks, this will affect the ratings of many of the symptoms. It is recommended to consider the total amount of time during the past week that the panic attack symptoms occurred, as well as their severity. For example, a participant who has few severe but short –lived panic attacks during the week, but who otherwise does not have many anxiety symptoms, would probably not have a very high total SIGH-A score.

NOTE: When rating items 8-11 and 13 the interviewer should rate symptoms regardless of whether they did (or did not) occur during a panic attack. Simply rate the symptom as it occurred over the past week.

Scoring: Summing each individual item leads to total scores ranging from 0 to 56.

## Structured Interview Guide for Hamilton Depression Scale (SIGH-D)

Purpose: To measure depression symptoms and their severity.

**Instructions:** The first question for each item should be asked as written. Follow-up questions are provided for further exploration or additional clarification of symptoms. The specified questions should be asked until enough information is provided to rate the item confidently. Follow-up questions may be added obtain necessary information. If the answer to a specified question is already known, it is sufficient to confirm the information with the subject (e.g., "You said that..."), make the rating, and continue. The final score for each item should reflect an assessment and balancing of the severity and frequency of the symptom. Note that participants with chronic symptoms may not be able to identify a period of normalcy or may report that "depressed" is their usual state. However, depression should not be rated as "normal" (i.e., a rating of "0") in these cases. Summing each individual item leads to total scores ranging from 0 to 53.

# Example:

# What's your mood been like this past week (compared to when you feel OK)?

Have you been feeling down or depressed? Sad? Hopeless? Helpless? Worthless? IF YES: Can you describe what this feeling has been like for you? How bad is the feeling?

Have you been crying at all?

**How have you been feeling about the future?** (optimistic/pessimistic) Do you feel better with encouragement/reassurance from others? Do you feel things will get better, improve, work out?

**IF DEPRESSED: In the past week, when something good, even small things have happened, did your mood brighten up?** How long did this brighten mood last? Were there things that occurred that should have brightened your mood but did not? In the last week, how often have you felt (OWN EQUIVALENT)? Every day? All day?

Inventory of Statements about Self-Injury (ISAS): The ISAS was designed to measure the occurrence and frequency of 12 methods of non-suicidal self-injury (NSSI; Section I. Behaviors), in addition to assessing 13 functions of NSSI (Section II. Functions). In the present study, we are only utilizing Section I to determine presence and frequency of NSSI behaviors (current and past) among participants. The ISAS has shown good validity and reliability (Klonsky & Glenn, 2008).

Multidimensional Emotional Disorder Inventory (MEDI; Rosellini, 2013) is a 50-item self-report measure designed to assess transdiagnostic vulnerabilities consistent with a dimensional approach. The MEDI is representative of a transdiagnostic assessment approach that is well suited for treatment planning and outcome monitoring for shared mechanism treatments like the UP (Rosellini, Boettcher, Brown, & [name], in press). The MEDI assesses neurotic temperament, positive temperament, depression, autonomic arousal, somatic anxiety, intrusive cognitions, social concerns, traumatic re-experiencing, and avoidance.

# IV. Higher-Order & Skills-Based Mechanisms

Anxiety Control Questionnaire Revised (ACQ-R): The ACQ-R is an 18-item measure designed to assess perceptions of control over potentially threatening internal and external events and situations associated with anxious responding (Brown et al., 2004; Rapee et al., 1996).

Beliefs about Emotions Scale (BES): The BES consists of 12 items and is designed to assess negative beliefs about emotions. Responses are rated on a scale from 0 (totally disagree) to 6 (totally agree). There is empirical support for its validity, reliability, and sensitivity to change (Rimes & Chadler, 2009).

*Difficulties in Emotions Regulation Scale (DERS):* The DERS is a 36 item self-report measure developed to assess clinically relevant difficulties in emotion regulation. DERS items aim to measure participants' difficulties with (a) awareness and understanding of emotions; (b) acceptance of emotions; (c) the ability to engage in goal-directed behavior, and refrain from impulsive behavior when experiencing negative emotions; and (d) access to emotion regulation strategies perceived as effective (Gratz & Roemer, 2004).

Eysenck Personality Questionnaire Revised – Short Form (EPQR-S): The EPQR-S is a commonly used 48 item personality inventory that consists of four subscales of 12 items each: Extraversion, Neuroticism, Psychoticism, and a Lie scale. In this study, we will administer the Extraversion and Neuroticism subscales, totaling 24 items (Brown, 2007).

UP Cognitive Skills Questionnaire (UP-CSQ): The UP-CSQ consists of 7 items. Participants are asked to rate the extent to which they used a variety of cognitive skills over the past week (e.g., "I looked for alternative explanations when I had distressing thoughts") on a scale from 1 (never)

to 5 (always or when needed). Items are summed to produce a total score, with higher scores indicating greater skill use. The UP-CSQ has recently been developed as a measure of cognitive skills in our research lab at the Center for Anxiety and Related Disorders. Preliminary data suggests psychometric properties of this measure are promising, however, further exploration of the validity, reliability, and use within an AUD population are necessary and will be explored in this trial (Woods, Conklin, Cassiello-Robbins, Sauer-Zavala; In Press).

Personality Assessment Inventory – Borderline Features Scale (PAI-BOR): The PAI-BOR is a 24-item measure that is based off a 4-factor model of borderline personality disorder. These factors, identified by Jackson and Trull (2001), are affective instability, identity disturbance, negative relationships, and self-harm (Morey, 1991).

The Personality Inventory for DSM-5 – Brief Form (PID-5-BF): The PID-5-BF is a 25-item personality trait assessment scale for adults age 18 or older. This measure assesses five personality trait domains: negative affect, detachment, antagonism, disinhibition, and psychoticism (Krueger et al., 2011).

Multidimensional Experiential Avoidance Questionnaire (MEAQ): The MEAQ is a self-report questionnaire that measures experiential avoidance, which is a tendency to avoid negative internal experiences, and is an important concept in numerous conceptualizations of psychopathology. Further, the MEAQ is broadly associated with psychopathology and quality of life (Gamez et al., 2011).

Anxiety Sensitivity Index (ASI): The ASI is a 16-item questionnaire designed to assess fear of anxiety-related symptoms (Reiss et al., 1986).

Southampton Mindfulness Questionnaire (SMQ): The SMQ is a 16-item measure of mindful awareness of distressing thoughts and images (Chadwick et al., 2008).

Distress Tolerance Scale (DTS; Simons & Gaher, 2005): The DTS is a self-report index of emotional distress tolerance with 15 items and 4 subscales. The subscales include tolerance (emotional distress tolerance), attraction (attraction to negative emotions), assessment (mental assessment of distress), and regulation (regulation of measures to sooth distress). Cronbach's alpha for the scales was 0.72, 0.82, 0.78, and 0.70, respectively, with a total  $\alpha$  of 0.82. In addition, criterion reliability and preliminary correlations were acceptable (Simons & Gaher, 2005).

Cognitive Emotion Regulation Questionnaire (CERQ-Short): The CERQ-short is a self-report measure of cognitive emotion regulation strategies used when responding to a stressful life event. The CERQ-short is a brief 18-item version of the original CERQ 36 item measure. The CERQ-

short has nine, two-item subscales. Five of the scales assess maladaptive and adaptive regulatory responses. Participants rate how often statements apply to them on a five-point scale from 1 "almost never", to 5 "almost always". Alpha coefficients for the short scales range from 0.68 (Self-blame) to 0.81 (Positive appraisal and Catastrophizing; Garnefski & Kraaij, 2006; Garnefski et al., 2006).

# V. Potential Moderators of Treatment Outcome

Credibility/Expectancy Questionnaire: The Credibility/Expectancy Questionnaire is a scale for measuring treatment expectancy and rationale credibility (Devilly & Borkovec, 2000).

Readiness to Change Questionnaire (RTCQ): The RTCQ is based on Prochsaka and DiClemente's (1986) stages of change model that is commonly utilized to resolve addictive tendencies, and is comprised of three stages: precontemplation, contemplation, and action. This questionnaire is therefore commonly used with excessive drinkers to measure their readiness to change. The RTCQ shows good validity and reliability (Rollnick et al., 1992).

Work and Social Adjustment Scale (WSAS): The WSAS is a five-item measure asking participants to rate the degree of interference caused by their symptoms in work, home management, private leisure, social leisure, and family relationships. Interference is rated over the past week on a 0 to 8 scale (0 = not at all interfering, to 8 = severe interference). The WSAS is a descriptive measure of subjective interference in various domains of living (Marks, Connolly, & Hallam, 1973).

*State Hope Scale (SHS*): The SHS is a 6-item measure of state and trait forms of optimism. The SHS provides scores for agency (i.e., "perceived capacity for initiating and maintaining the actions necessary to reach a goal") and pathways (i.e., "perceived ability to generate routes to one's goals") as well as general state hope. The SHS is an internally consistent measure whose scores have demonstrated convergent and discriminant validity in relation to theoretically meaningful measures. Responses to the SHS were made on an eight-point scale ranging from definitely false (1) to definitely true (8) (Snyder et al., 1996).

# **VI. Other Measures**

Homework Compliance Scale: At the end of each session, the therapist will evaluate the degree of homework compliance for each participant on a 0-6-point compliance scale. An overall average rating will be obtained for each participant by summing the scores for all sessions and dividing them by the number of sessions attended (Primakoff, Epstein & Covi, 1986).

Treatment Skills Usage Questionnaire: The Treatment Skills Usage Questionnaire is a 10-item questionnaire that asks each participant about the coping skills he/she/they may or may not have learned over the course of treatment. The questionnaire is specifically concerned with

determining the skills that the participants has managed to consistently utilize since ending treatment.

Working Alliance Inventory-Short Form-Therapist Version (WAI-SF): The WAI-SR is a 12-item questionnaire that assesses therapeutic alliance and is completed by the therapist: 1) agreement between participants and therapist on the goals of the treatment; 2) agreement between participants and the therapist about the tasks to achieve these goals; and 3) the quality of the bond between the participant and therapist (Tracey & Kokotovic, 1989).

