#### Allowance for Missed/Rescheduled Sessions:

• TC: Participants will receive 12 treatment sessions in 12 to 16 weeks.

• UP: Participants will receive 16 treatment sessions in 16 to 21 weeks.

Participants will have two weeks from the target date to complete each assessment. If a participant fails to contact study personnel for two consecutive weeks, he/she will be withdrawn from the study and informed of study withdrawal via letter sent to his/her home address.

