### **Therapist Assessments Procedures**

The therapist is responsible for completing the Homework Compliance Scale (HCS) after each session. For the Take Control condition, there is never assigned HW, and for certain sessions of the UP there is not assigned HW. In these instances the therapist should still complete the HCS and select "0-Homework was not assigned". In addition to completing the HCS every session the study therapist should complete the Working Alliance Inventory-Short Form-Therapist Version (WAI-SFT) at sessions 4, 8, 12, and 16. The Clinical Global Impression-Improvement and Severity Scales (CGI-I and CGI-S) should be completed in Qualtrics at session 1, 4, 8, 12, and 16 (the IEs will complete the CGI and CGs at post-assessment, 1-month, and 6month follow-ups). To complete these assessments the therapist should go into the StAR2 Qualtrics folder and select the session number. Within the session folder there is a Therapist Assessment survey battery which includes all the assessments that need to be completed for each session.

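### The homework compliance average counts sessions without homework as zeros, so every Take Control participant scores 0 and Unified Protocol scores are shrunk

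*Combined protocol and SAP*

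**What the plan says.** The Homework Compliance Scale (HCS) is described under VI. Other Measures. At the end of each session, "the therapist will evaluate the degree of homework compliance for each participant on a 0-6-point compliance scale". The participant's overall rating comes from "summing the scores for all sessions and dividing them by the number of sessions attended".

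Therapist Assessments Procedures repeats that "The therapist is responsible for completing the Homework Compliance Scale (HCS) after each session" and then covers sessions without homework: "For the Take Control condition, there is never assigned HW, and for certain sessions of the UP there is not assigned HW". It continues: "In these instances the therapist should still complete the HCS and select '0-Homework was not assigned". The form is thus completed at every session in both arms, and a session without homework leaves a numeric 0 in the data rather than a blank.

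The planned numbers of sessions are given under Allowance for Missed/Rescheduled Sessions: "TC: Participants will receive 12 treatment sessions in 12 to 16 weeks" and "UP: Participants will receive 16 treatment sessions in 16 to 21 weeks".

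No section says that the code for no homework is to be treated as missing, or that such sessions leave the numerator or the denominator. The documents state only what the code 0 means; they give no other anchors of the scale.

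**The concern.** The averaging rule and the coding instruction each make sense alone, but they do not fit together. The average takes in all sessions and divides by attendance. The coding instruction puts a number on the same 0-6 axis at sessions where there was no compliance to judge. Followed literally, each such session adds 0 to the sum and 1 to the divisor.

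What is at stake is the meaning of one score. In TC it would be a constant that carries no information about behaviour. In UP it would mix two things, how well assigned homework was done and what share of attended sessions had homework to rate. A reader of a UP adherence table would see compliance understated, and could not tell by how much without the per-session codes.

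**Working it through.** **Inputs from the documents.** Scale range 0 to 6, rated at each session (VI. Other Measures). Code 0 entered when homework was not assigned; homework never assigned in TC and not assigned at some UP sessions (Therapist Assessments Procedures). Planned sessions: 12 in TC and 16 in UP (Allowance for Missed/Rescheduled Sessions).

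**Input not in the documents.** The number k of UP sessions without homework. The only statement is that "for certain sessions of the UP there is not assigned HW", so k is above zero but otherwise unknown. I assume k = 1 to 4 of 16 to show a range.

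The plan states no numerical HCS result, so there is no figure to reproduce. The check applies the written rule directly.

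**Formula.** Let m be the mean rating over attended sessions that had homework, n the sessions attended, and k the attended sessions without homework.

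- Rule as written: score = [m × (n − k) + 0 × k] / n = m × (n − k)/n.
- Divisor limited to sessions with homework: score = m × (n − k)/(n − k) = m, undefined when k = n.

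**TC.** Here k = n, so the written rule gives 0/12 = 0.00, and likewise 0 for any other number of sessions attended. With the limited divisor the score is 0/0, that is, not applicable.

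**UP completer, n = 16, k assumed.**

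| k | Shrinkage k/16 | Score if m = 6 | Score if m = 5 | Score if m = 4 |
|---|---|---|---|---|
| 1 | 6.25% | 6 × 15/16 = 5.63 | 4.69 | 3.75 |
| 2 | 12.5% | 6 × 14/16 = 5.25 | 4.38 | 3.50 |
| 3 | 18.75% | 6 × 13/16 = 4.88 | 4.06 | 3.25 |
| 4 | 25% | 6 × 12/16 = 4.50 | 3.75 | 3.00 |

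The column m = 6 is the highest score that a fully compliant participant can reach. With the limited divisor each entry returns to m.

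**Different attendance, same compliance (assumed patterns, m = 5).** A completer with k = 2 of 16 scores 5 × 14/16 = 4.38. A participant who stops after 4 sessions, 2 of them without homework, scores 5 × 2/4 = 2.50. If none of those 4 sessions lacked homework, the same participant would score 5 × 4/4 = 5.00. For early leavers the size of the shrinkage relative to completers, and even its direction, depends on where the sessions without homework fall. The documents do not say where.

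**The case against.** The strongest reply is that this is a minor measure which nobody plans to analyse. That is largely right. The Data Analysis Aims, the fMRI Aims and the hypotheses under Research Design do not mention homework compliance, and the scale sits under Other Measures rather than among the potential moderators. No section plans a comparison of the arms on it or a dose-response analysis. A reader might infer that the trial's efficacy conclusions, or a planned adherence analysis, are compromised; the documents do not support that. A zero in TC is also unlikely to mislead anyone who knows that TC sets no homework.

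A reader might also infer that sessions without homework are scored as total non-compliance. The documents do not say so. They attach only one meaning to 0, that no homework was assigned, and homework set but not done may be coded 1 or higher. What can be said is that the code enters the average at the floor of the scale, so such a session pulls the average down at least as much as the worst true rating could.

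Third, if the sessions without homework are fixed by the treatment manual, all 16-session completers share the same k. Their scores are then multiplied by one constant, (16 − k)/16, which leaves ranks and correlations among completers unchanged. This stands, so it would be too strong to say that every use of the score in UP is invalid. It does not rescue the absolute level, nor comparisons that include people who attended fewer sessions.

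Finally, an analyst could filter the zeros, since the codes are recorded session by session. That makes the problem easy to repair, but the written rule includes all sessions and divides by attendance, so following it still yields the wrong number.

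**Conclusion.** The point holds as a scoring error of limited reach. The averaging rule and the coding instruction together give a structural 0 for every TC participant and a UP score shrunk by k/n. That k is above zero in the UP programme follows from the text; its size does not. Under the assumed 1 to 4 sessions of 16, the loss is 6.25% to 25% and the ceiling falls from 6 to between 5.63 and 4.50. Among UP completers the effect may be a constant scale factor. Distortion between participants arises mainly for those who attend fewer sessions, or if k varies.

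The harm is confined to the compliance score and to any adherence description or secondary use of it. The primary outcome and the stated aims are untouched. This is a worthwhile clarification, not a threat to the trial.

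**What to change.** First, check the HCS form to confirm that 0 is used only when homework was not assigned. This matters because, if 0 can also record homework set but not done, turning every 0 into not applicable would delete real non-compliance and inflate the UP scores. In that case, use a separate not-applicable flag.

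Then amend the scoring rule under VI. Other Measures: treat sessions without homework as not applicable; divide the summed ratings by the number of attended sessions at which homework compliance could be rated; and report the score for UP only, with TC shown as not applicable. Reporting the number of ratable sessions beside the average would show how much data each score rests on.

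If 0 has the single meaning, the cost is one sentence in the scoring rule and no new data, because the per-session codes are already recorded. If 0 carries two meanings, a flag must be added to the form, and sessions already coded would need to be classified from session records where these allow it.
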